4.1.1.3.3 Unsolicited Adverse Events

In addition to recording solicited reactions, parents / guardians will be instructed to record any other medical events that may occur during the 30-day period after each vaccination. Space will be provided in the diary card for this purpose.

Information on SAEs will be collected and assessed throughout the study, from the time of vaccination until 6 months after the last vaccination. Any SAE occurring at any time during the study will be reported by the Investigator in the CRB according to the completion instructions provided by the Sponsor; this includes checking the "Serious" box on the AE case report form (CRF) and completing the appropriate Safety Complementary Information CRFs. All information concerning the SAE is to be reported either as part of the initial reporting or during follow-up reporting if relevant information became available later (e.g., outcome, medical history, results of investigations, copy of hospitalization reports). In case a subject experiences febrile convulsion (neurological event associating fever and seizure), the assessment will be performed according to the "Guideline for definition and collection of cases of febrile convulsion", and this event will be considered an SAE. See the protocol for further details on SAE reporting.

For each unsolicited AE (whether serious or non-serious), the following information is to be recorded:

- Start and stop dates^a
- Intensity of the event:

- Intensity of the event

- For measurable unsolicited AEs that are part of the list of solicited reactions, the size of the AE as well as the temperature for fever will be collected and analyzed based on the corresponding scale used for solicited reactions (see Table 4.1 and Table 4.2).
- All other unsolicited AEs will be classified according to the following intensity scale:
 - Grade 1: A type of AE that is usually transient and may require only minimal treatment or therapeutic intervention. The event does not generally interfere with usual activities of daily living.
 - Grade 2: A type of AE that is usually alleviated with additional therapeutic intervention. The event interferes with usual activities of daily living, causing

_

The stop date of all related AEs will be actively solicited. For other events, the Investigator will provide the stop date when it becomes available. AEs for which no stop date was obtained during the course of the study will be considered as ongoing at the end of the study.

discomfort but poses no significant or permanent risk of harm to the research participant.

- Grade 3: A type of AE that interrupts usual activities of daily living, or significantly affects clinical status, or may require intensive therapeutic intervention.
- Whether the AE was related to the investigational product (for unsolicited systemic AEs)
 - The Investigator will assess the causal relationship between the AE and the investigational product as either "Not related" or "Related", as described in Section 4.1.1.3.6.

Action taken for each AE (e.g., medication)

- The action(s) taken by the parent / guardian to treat and/or manage any unsolicited AEs will be classified in the CRB using the following list (all applicable items should be checked):
 - None
 - Medication
 - Health care provider contact
 - Hospitalized
 - Discontinuation of study vaccination
- Whether the AE was serious
 - For each SAE, the Investigator will complete all seriousness criteria that apply (outcome, elapsed time, and relationship to study procedures).
- Whether the AE caused study discontinuation

4.1.1.3.4 Adverse Events of Special Interest

An AESI is defined as an event for which ongoing monitoring and rapid communication by the Investigator to the Sponsor must be done. The following AEs will be captured as AESIs throughout the study:

- Generalized seizures (febrile and non-febrile)
- Kawasaki disease
- Guillain-Barré syndrome
- Idiopathic thrombocytopenic purpura (ITP)

These events have been listed as AESIs based on the feedback received from the European Union regulators.

No safety concerns relating to these AESIs have been identified with the use of MenACYW conjugate vaccine in the completed clinical trials. Because of their medical importance and to ensure expedited communication to the Sponsor, these AESIs are to be considered and collected as SAEs and reported to the Sponsor according to the procedure described in the protocol. Further

instructions on the data collection for these events and the relevant definitions will be provided in the Operating Guidelines.

4.1.1.3.5 Medically-Attended Adverse Events

MAAE information will be collected throughout the study. MAAEs will be recorded as unsolicited AEs for up to D30 after each vaccination and as MAAEs until the next study visit on the appropriate diary cards. MAAEs that occur from D31 after the last vaccination visit until the 6-month follow-up phone call will be recorded in the appropriate memory aid. An MAAE that occurs within the study period but meets the definition of an SAE should be reported only on the SAE Reporting Form but not on the MAAE page of the CRB.

The Investigator will assess the causal relationship between the MAAE and the investigational or study product as either "Not related" or "Related", as described in Section 4.1.1.3.6.

4.1.1.3.6 Assessment of Causality

The Investigator will assess the *causal relationship* between each unsolicited systemic AE and the product administered as either *not related*, based on the following definitions:

- Not related The AE is clearly / most probably caused by other etiologies such as an
 underlying condition, therapeutic intervention, or concomitant therapy; or the delay between
 vaccination and the onset of the AE is incompatible with a causal relationship; or the AE
 started before the first vaccination (screening phase, if applicable)
- Related There is a "reasonable possibility" that the AE was caused by the product administered, meaning that there is evidence or arguments to suggest a causal relationship

Note: By convention, all AEs reported at the injection site (whether solicited or unsolicited) and all solicited systemic AEs are considered to be related to the administered product and therefore are referred to as reactions and do not require the Investigator's opinion on relatedness.

AEs likely to be related to the product, whether serious or not, that persist at the end of the study will be followed up by the Investigator until their complete disappearance or the stabilization of the subject's condition. The Investigator will inform the Sponsor of the date of final disappearance of the event or the date of "chronicity" establishment.

4.2 Derived Endpoints: Calculation Methods

4.2.1 Safety

4.2.1.1 Solicited Reactions

4.2.1.1.1 Daily Intensity

All daily records for solicited reactions will be derived into daily intensity according to the following classification: None, Grade 1, Grade 2, Grade 3, or Missing (Unknown).

For the derivation of daily intensities, the following sequential steps will be applied:

- 1) Solicited reactions (except Fever/Pyrexia) with CRF presence recorded as "No" and with all daily records missing (Unknown), then all daily intensities will be derived as None.
- 2) For non-measurable (NM) solicited reactions, daily intensities will correspond to daily records reported in the clinical database. For measurable solicited reactions, the daily measurements reported in the clinical database will be converted based upon the intensity scales defined in the protocol; this assumes a reaction that is too large to measure (NM) is Grade 3. Note the intensity could be considered "None" (not a reaction) in the analysis despite being considered a reaction by the investigator.

Note: The maximum intensity on the ongoing period is derived from the record of the maximum intensity/measurement after the end of the solicited period following the rule described above.

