13.2 Source Data and Source Documents

"Source data" are the data contained in source documents. Source documents are original documents or certified copies, and include, but are not limited to, diary cards, medical and hospital records, screening logs, informed consent / assent forms, telephone contact logs, and worksheets. The purpose of study source documents is to document the existence of subjects and to substantiate the integrity of the study data collected. Investigators must maintain source documents so that they are accurate, complete, legible, and up to date.

For missing or discrepant data on a diary card, the study coordinator will obtain verbal clarification from the subject, enter the response into the "Investigator's comment" page of the diary card, and transfer the information to the CRB.

The subject pre-screening log should list all individuals contacted by the Investigators to participate in the study, regardless of the outcome.

The Investigator must print^a any electronic records on an ongoing basis, sign and date them immediately after creation, and keep the printouts on file as source documents that can be verified by the Sponsor or an inspector against the electronic records. Any subsequent changes of an

^a Unless the electronic medical records are managed by validated computerized systems that are compliant with US 21 CFR Part 11, in which case they are acceptable on their own.

electronic record require the record to be re-printed, dated (with an indication of the date of change), and signed. Such records must also be kept together with the original printed copy.

Good Documentation Practice should be followed by the Investigator and the site staff managing source documents.

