4.2.1.1.2 Maximum Overall Intensity

Maximum overall intensity is derived from the daily intensities computed as described in Section 4.2.1.1.1 and is calculated as the maximum of the daily intensities over the period considered.

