4.2.1.1.3 Presence

Presence is derived from the maximum overall intensity on the period considered:

- None: No presence
- Grade 1, Grade 2, or Grade 3: Presence
- Unknown: Missing presence

Subjects with at least one non-missing presence for a specific endpoint will be included in the safety analysis. Conversely, those without a non-missing presence will not be included in the safety analysis of the endpoint.

The time period is displayed as D0-D3, D4-D7, D8 and later.

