4.2.1.5.5 AEs Leading to Study Discontinuation

This information will be summarized as collected. A flag is available in the clinical database for all AEs in order to identify AEs leading to discontinuation.

In general, the items that are counted are:

- Disposition table: A subject who on the "Completion at End of Study" form
- question "What was the participant's status?" has "Adverse Event" checked.
- Safety overview table: A subject who either on the "Completion at End of Study" form, question" What was the participant's status?" has "Adverse Event" checked or lists a solicited AE that has "Caused Study Termination" checked that is at least Grade 1 or an unsolicited AE that has "Caused Study Discontinuation" checked that is at least Grade 1 or missing and is within the time period indicated.
- System Organ Class/Preferred Term (SOC/PT) table: A solicited AE that has "Caused Study Termination" checked that is at least Grade 1 or an unsolicited AE that has "Caused Study Discontinuation" checked that is at least Grade 1 or missing and is within the time period indicated.

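### For the eight non-fever solicited reactions, an infant flagged 'No' without daily records is kept as a non-reactor, while an infant flagged 'Yes' without daily records is left out of the endpoint

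*SAP*

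**What the plan says.** SAP 4.2.1.1.1 derives daily intensities in two sequential steps.

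- **Step 1** applies to every solicited reaction except fever. With the CRF presence flag at 'No' "and with all daily records missing (Unknown), then all daily intensities will be derived as None".
- **Step 2** covers everything else and does not mention the flag. For reactions graded by the parent, "daily intensities will correspond to daily records reported in the clinical database". Redness, swelling and temperature are converted from the recorded measurements, and a reaction too large to measure is taken as Grade 3.

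The later derivations build on those daily values. Under SAP 4.2.1.1.2 the maximum overall intensity "is calculated as the maximum of the daily intensities over the period considered". Under SAP 4.2.1.1.3, "Presence is derived from the maximum overall intensity on the period considered". An unknown maximum gives missing presence, and "those without a non-missing presence will not be included in the safety analysis of the endpoint".

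SAP 5.3.1.4 refers missing solicited intensities back to 4.2.1.1.1. SAP 5.3.1 says in general that nothing is replaced.

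**The concern.** Two infants can have the same gap in the diary, with no daily entry for a reaction, and differ only in the flag. The one reported without the reaction is kept and counted as zero. The one reported with it leaves both numerator and denominator. The SAP therefore relies on the flag when it is negative and ignores it when it is positive.

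The situation can plausibly arise. For redness and swelling the parent records only a size, so a reaction that was seen but not measured has no gradable entry. The first two diary cards are collected about 60 days after vaccination and the third about six months after. Someone asked at that point may remember that a reaction occurred without being able to reconstruct daily grades or millimetres.

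The SAP handles unsolicited events differently. Under 4.2.1.2.1 an event needs a verbatim term and must not be Grade 0, so a missing intensity does not remove it. In 4.2.1.5.5 a solicited reaction leading to discontinuation must reach Grade 1, whereas an unsolicited event counts if it is one "that is at least Grade 1 or missing and is within the time period indicated".

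Describing safety is the study's only objective, and solicited reaction percentages with exact confidence intervals are among its main outputs. A rule that discards reported reactions bears directly on them.

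**Working it through.** The plan states no figure on this point, so there is none to reproduce. The check has two parts.

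**1. The rule applied as written, all daily records missing**

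| CRF presence flag | Non-fever reaction | Fever |
|---|---|---|
| 'No' | No presence (counted as zero) | Missing (excluded) |
| 'Yes' | Missing (excluded) | Missing (excluded) |
| Blank | Missing (excluded) | Missing (excluded) |

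The asymmetry between 'Yes' and 'No' exists only in the non-fever column. SAP Tables 4.1 and 4.2 list 3 injection site and 6 systemic reactions, 9 in all. Without fever, 8 are affected.

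The ongoing-period derivation in SAP 4.2.1.1.7 does not recover the 'Yes' infants. It requires the last daily intensity of the solicited period to be at least Grade 1, and here that value is missing.

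**2. Size under assumed values**

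Let p be the true reaction rate and m the share of reactors flagged 'Yes' with no daily records. Both are assumptions; neither is in the documents. If no non-reactor is dropped,

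reported rate = p(1 − m) / (1 − pm).

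For p = 30%:

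- m = 2%: 0.294 / 0.994 = 29.6%
- m = 5%: 0.285 / 0.985 = 28.9%
- m = 10%: 0.270 / 0.970 = 27.8%

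Over p from 5% to 50% and m from 1% to 10%, the shift runs from −0.05 to −2.63 percentage points.

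For scale, the exact 95% interval for 693/2310 (30% of Group 1) is 28.1% to 31.9%, a half-width of about 1.9 points. The shift at p = 30% is 0.4, 1.1 and 2.2 points for m = 2%, 5% and 10%, so only m = 10% exceeds that half-width. In Group 2 (n = 770) the half-width is about 3.3 points, and none of the three exceeds it.

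**Between-group difference.** With the same p and m in both arms the formula gives the same reported rate in each, so the difference stays at zero. If m = 5% in one arm and 0 in the other, the difference moves by 50 − 48.72 = 1.28 points at p = 50% and by 20 − 19.19 = 0.81 points at p = 20%.

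**If non-reactors are also dropped.** Let q be the share of non-reactors excluded, for example because the flag is blank as well. Then

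reported rate = p(1 − m) / [p(1 − m) + (1 − p)(1 − q)].

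This equals p when m = q. With p = 30%, m = 2% and q = 5% it is 0.294 / (0.294 + 0.665) = 30.7%, above the true rate.

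**The case against.** The strongest reply is that 'Yes' and 'No' are not mirror images. A 'No' fully answers the endpoint question, because there is nothing to grade, and blank daily fields may be the normal entry for a non-reactor. A 'Yes' with no grade or size is an incomplete record. This is right as a defence of step 1, which is reasonable in itself. It does not justify excluding the 'Yes' infant from a percentage that asks only whether the reaction occurred.

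Second, such records are targeted before analysis. Protocol 13.2 states: "For missing or discrepant data on a diary card, the study coordinator will obtain verbal clarification", with the answer transferred to the CRB. Protocol 11.1 and 11.2 add diary review and consistency checks, and 13.4.1 requires queries to be completed before database lock. This stands as a reason to expect few cases. It does not change what the rule does with those that remain.

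Third, the SAP prefers measurements to the investigator's opinion: 4.2.1.1.1 allows a recorded reaction to be analysed as none, and 4.2.1.1.7 sets aside the investigator's ongoing flag. That principle governs values that were recorded; here none were.

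Two stronger readings are tempting, and the documents support neither.

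- A reader might infer that missing diary data as a whole bias reaction rates downward. Infants with a blank flag and no records are also excluded and may be non-reactors, so the net direction depends on m and q, both unknown.
- A reader might infer that a 'Yes' infant with one day recorded as none and the rest missing is counted as a non-reactor. That is one reading of 4.2.1.1.2, but the section does not say how missing days enter the maximum. Counting all such infants as reactors would let the flag override days actually recorded as none.

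**Conclusion.** The point holds in a limited form. For the eight non-fever solicited reactions, the SAP keeps 'No' without daily records as a non-reaction and excludes 'Yes' without daily records. Within the group of infants who have a flag but no daily records, this lowers the reported reaction percentage in each arm.

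The size is not known, because the documents give no frequency. The 0.4 to 2.2 point range at p = 30% rests on assumed values of m from 2% to 10% and on no non-reactor being dropped. Given the data queries, the true effect is probably towards the small end or below it. The comparison between groups is unaffected if reaction rates and missingness are equal across arms. Fever is outside the point, since 'Yes' and 'No' without temperatures are both excluded. The change is worth making because the rule discards reactions that were reported and the remedy is cheap.

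**What to change.** In SAP 4.2.1.1.1 and 4.2.1.1.3, add: for a non-fever solicited reaction with CRF presence 'Yes' and all daily records missing, the subject counts as having the reaction, with maximum intensity, time of onset and number of days of occurrence shown as missing. Report the number of such cases by group and dose, so that the size of the effect is visible.

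Leave infants with any recorded daily value, and all fever data, on the existing measurement-based rule.

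The cost is a sentence in the SAP and a small programming change that uses a field already collected. The downsides are a missing-intensity row in the tables and slightly higher reported reaction rates.

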4.2.1.1.2 Maximum Overall Intensity

Maximum overall intensity is derived from the daily intensities computed as described in Section 4.2.1.1.1 and is calculated as the maximum of the daily intensities over the period considered.

4.2.1.1.3 Presence

Presence is derived from the maximum overall intensity on the period considered:

- None: No presence
- Grade 1, Grade 2, or Grade 3: Presence
- Unknown: Missing presence

Subjects with at least one non-missing presence for a specific endpoint will be included in the safety analysis. Conversely, those without a non-missing presence will not be included in the safety analysis of the endpoint.

The time period is displayed as D0-D3, D4-D7, D8 and later.

4.2.1.1.4 Time of Onset

Time of onset is derived from the daily intensities as described in Section 4.2.1.1.1. It corresponds to the first day with intensity of Grade 1, Grade 2, or Grade 3.

Note: If a reaction is not continuous (i.e., reaction occurs over two separate periods of time intervened by at least one daily intensity Missing or None) then the time of onset is the first day of the first occurrence.

4.2.1.1.5 Number of Days of Occurrence during the solicited period

Number of days of occurrence over the period considered is derived from the daily intensities computed as described in Section 4.2.1.1.1. It corresponds to the number of days with daily intensities of Grade 1, Grade 2, or Grade 3. Number of days of occurrence on the solicited period with a specified intensity may also be derived.

4.2.1.1.6 Overall Number of Days of Presence

If a reaction is ongoing at the end of the solicited period, then the overall number of days of presence is derived from the daily intensities and the end date of the reaction after the end of the solicited period. The overall number of days of presence is:

• (End date – last vaccination date) + (number of days of occurrence within the solicited period) – length of the solicited period + 1

If the end date of the solicited reaction is missing or incomplete (contains missing data), the overall number of days of presence will be considered as Missing.

4.2.1.1.7 Ongoing

Ongoing is derived from the last daily intensity of the solicited period computed as described in Section 4.2.1.1.1 and the maximum intensity on the ongoing period. The investigator's ongoing flag is not used because the measurement would determine the ongoing status of the reaction.

- Ongoing: if the last daily intensity of the solicited period is at least Grade 1 and the maximum intensity on the ongoing period is at least Grade 1
- Not ongoing: if the last daily intensity of the solicited period is None or the maximum intensity on the ongoing period is None.
- Missing: all other conditions (in this case, it is not included in the denominator of the ongoing analysis in the safety tables)

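### SAP 4.2.1.1.7 drops a solicited reaction still present on D07 from the ongoing analysis when no later intensity is recorded, even if the end date or the investigator's flag shows that it continued

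*SAP*

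**What the plan says.** SAP 4.2.1.1.7 sorts each reaction into three states.

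- **Ongoing** requires Grade 1 or more both on D07 and in the later maximum.
- **Not ongoing** requires only that one of these two values is None.
- **Missing** takes every combination left over, which the SAP words as "all other conditions (in this case, it is not included in the denominator of the ongoing analysis in the safety tables".

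On the investigator's own view, the section says that the "ongoing flag is not used because the measurement would determine the ongoing status of the reaction".

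SAP 4.2.1.1.1 takes the post-D07 intensity from a single record of the maximum after the solicited period. For reactions other than fever, it also sets every day to None when the CRF says that the reaction was absent and all daily records are missing. SAP 5.3.1 allows no replacement of missing data.

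The end date appears only in SAP 4.2.1.1.6, which uses it to count days: "If a reaction is ongoing at the end of the solicited period, then the overall number of days of presence is derived". It plays no part in deciding the status.

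**The concern.** The SAP sets the flag aside because a measurement settles the matter. That is reasonable when a post-D07 value exists. When it does not, nothing settles the matter, yet the flag and the end date stay unused. An infant with swelling on D07 and a recorded end date of D12 is treated as if nothing were known about persistence.

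The rationale also fits only part of the list if taken literally. Of the nine solicited reactions in SAP Tables 4.1 and 4.2, three are measured (fever, redness, swelling) and six are graded by the parent.

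The loss is selective. A blank post-D07 field costs nothing for an infant with None on D07, who stays Not ongoing. It removes an infant who still had the reaction. In a trial whose only objective is to describe safety, the table could then understate how often reactions outlast the diary week. If ongoing in SAP 4.2.1.1.6 means this status, the overall number of days of presence is also lost for reactions whose end date is known.

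**Working it through.** **1. The rule laid out.** Each intensity can be None, Grade 1 or more (G1+), or missing.

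| D07 | Post-D07 None | Post-D07 G1+ | Post-D07 missing |
|---|---|---|---|
| None | Not ongoing | Not ongoing | Not ongoing |
| G1+ | Not ongoing | Ongoing | **Missing** |
| missing | Not ongoing | **Missing** | **Missing** |

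The cell at issue is D07 G1+ with post-D07 missing. The end date or flag may resolve it, but the rule consults neither.

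**2. Inputs.** The documents state no percentage ongoing and no missingness rate, so there is no figure to reproduce and every rate below is assumed. Let t be the true proportion ongoing and m2 the share of ongoing reactions with no post-D07 intensity. Let m1P and m1N be the shares with D07 missing among infants truly ongoing and truly not ongoing. Infants not ongoing are taken to be None on D07 and, unless stated, to have a blank post-D07 field. The denominator is all assessed infants.

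Observed = t(1−m1P)(1−m2) / [t(1−m1P)(1−m2) + (1−t)(1−m1N)]

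**3. Only the post-D07 value missing.** With m1P = m1N = 0 and m2 = q, this becomes t(1−q)/(1−tq).

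- t = 5%, q = 10%: 0.045/0.995 = 4.52%
- t = 5%, q = 20%: 0.040/0.990 = 4.04%
- t = 5%, q = 30%: 0.035/0.985 = 3.55%
- t = 10%, same q: 9.09%, 8.16%, 7.22%

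**4. Direction.** The bias is downward only if (1−m1P)(1−m2) < (1−m1N). At t = 5%:

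- D07 also missing at the same rate in everyone: the D07 term cancels, and the results equal step 3.
- As above, but with post-D07 None recorded for every not-ongoing infant whose D07 is missing: 4.09%, 3.26%, 2.51% at 10%, 20%, 30%.
- D07 missing at random and post-D07 complete for ongoing reactions: 5.00%, no bias.
- D07 missing only in infants not ongoing: 0.05/(0.05 + 0.95×0.9) = 5.52% at 10%, and 0.05/(0.05 + 0.95×0.7) = 6.99% at 30%. The bias is upward.
- 20% of those not ongoing lack D07 and 10% of those ongoing lack the later value: 0.045/(0.045 + 0.95×0.8) = 5.59%, also upward.

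**5. Effect of the fallback.** At t = 5% and q = 20%, the current rule gives 4.04%. If the end date or flag resolves 50%, 80% or 100% of the unresolved ongoing reactions, the result is 4.52%, 4.81% or 5.00%.

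**6. Days of presence.** Take a reaction present on D05 to D07 (3 days) with end date D12. The formula in SAP 4.2.1.1.6, with an 8-day solicited period (D0 to D07), gives 12 + 3 − 8 + 1 = 8 days. It needs no post-D07 intensity. If the 4.2.1.1.7 status controls entry to it, this reaction has no duration although every term is known.

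**The case against.** Several objections carry weight.

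- **The asymmetry is ordinary logic.** A reader might infer that it is a flaw for one None to suffice for Not ongoing while Ongoing needs two positive values. It is not: that is the negation of a two-part condition. Only the unresolved cells are open to criticism.
- **Downward bias is not certain.** A reader might infer that the percentage must be too low and that the excluded cases are nearly all truly ongoing. The documents do not support that. Infants with both values missing also leave, as does a reaction that ended on D07 with nothing recorded later. Fever is exempt from the rule that sets absent reactions to None, so afebrile infants without temperatures leave too. Step 4 shows that the direction can reverse.
- **D07 missing with post-D07 Grade 1 or more can be indeterminate.** Had D07 been None, the rule would give Not ongoing. By the definition in SAP 4.1.1.1, an event starting on D08 is unsolicited.
- **Missing values may be few.** Site staff review diary cards with parents and clarify incomplete entries (protocol 11.1 and 13.2). Nothing shows how often an end date or flag exists without a later intensity.
- **The link to days of presence is one reading.** SAP 4.2.1.1.6 does not cite 4.2.1.1.7.
- **The stakes are limited.** Ongoing status is not among the endpoints in SAP 4.1.1.2 or in Table 5.2, no hypothesis is tested, and similar missingness would move both groups alike.

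These points narrow the claim and its importance. None explains why recorded evidence of continuation should be ignored when the value meant to replace it is absent.

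**Conclusion.** The point holds in a limited form. The rule as written classes a reaction of Grade 1 or more on D07 as Missing whenever the post-D07 maximum is not recorded, and so discards information that the SAP already uses or names. The percentage ongoing may then be biased, most likely downward, because a blank later field affects only infants not already None on D07 and because absent reactions other than fever are kept as None.

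On assumed inputs (true 5%, with 10% to 30% of ongoing reactions lacking the value), the table would show about 4.5% to 3.6%, or 0.5 to 1.4 percentage points too low. The SAP does not say whether the denominator is all assessed infants or only those with the reaction. In the latter case the true percentage is higher and the relative loss somewhat smaller: a true 20% would be seen as 18.4% to 14.9%.

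This is a desirable improvement to a supporting table. It does not threaten the trial's main safety description.

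**What to change.** In SAP 4.2.1.1.7, keep the current rule whenever both intensities are recorded or either is None, so that a recorded intensity always decides. Add a fallback for one case, D07 at Grade 1 or more with the post-D07 intensity missing:

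1. End date after D07: Ongoing.
2. End date on or before D07: Not ongoing.
3. No usable end date: follow the investigator's flag.
4. Neither available: Missing.

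Leave D07 missing with post-D07 Grade 1 or more as Missing in the main table, and count it as ongoing in a sensitivity analysis. Report the number Missing by group and reaction. State in SAP 4.2.1.1.6 whether ongoing there means this status.

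The intensities, end date and flag are already named in the SAP, so no new data are needed. The cost is some wording, a small extra derivation and one additional table. Percentages ongoing are likely to rise slightly.
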